8.2.1 Hepatic Toxicity

For ≥ grade 3 ALT or AST or Bilirubin (see Investigations in CTCAE v. 4.0), interrupt enzalutamide. Check liver function labs weekly. Restart enzalutamide at one dose level reduction when ALT, AST, and bilirubin recover to grade 1. Monitor serum transaminases and bilirubin every two weeks for three months and monthly thereafter.

For hepatic failure (see Hepatobiliary Disorders in CTCAE v. 4.0), discontinue enzalutamide.

8.2.2 Neurologic toxicity

Discontinue enzalutamide for any seizure.

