3.3.7 No History of the following

- Prior brain metastases
- Leptomeningeal disease
- Seizures
- Class 3 or 4 congestive heart failure
- Uncontrolled hypertension (systolic BP > 170mmHg or diastolic BP > 105 mmHg) despite optimal medical management
- Major surgery ≤ 4 weeks of registration

3.3.8 Required Initial Laboratory Values:

Absolute Neutrophil Count (ANC) $\geq 1,500/\text{mm}^3$

Platelet Count $\geq 100,000/\text{mm}^3$

Creatinine ≤ 1.5 x upper limit of normal (ULN) **OR**

Calc. Creatinine Clearance ≥ 30 mL/min

Total Bilirubin $\leq 1.5 \text{ x upper limit of normal (ULN)}$ AST / ALT $\leq 3.0 \text{ x upper limit of normal (ULN)}$

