7.0 TREATMENT PLAN/INTERVENTION

Enzalutamide will be given 160 mg orally once daily (1 cycle= 28 days). Dose interruptions and reductions are detailed in protocol Section 8.2. Patients will remain on therapy until progression of disease or development of unacceptable toxicities or patient or physician withdrawal.

Protocol treatment is to begin ≤ 7 days of registration.

It is acceptable for individual study drug doses to be delivered \leq a 24-hour (business day) window before and after the protocol-defined date for Day 1 of a new cycle. For example, if the treatment due date is a Friday, the window for treatment includes the preceding Thursday through the following Monday. In addition, patients are permitted to have a new cycle of chemotherapy delayed up to 7 days for major life events (e.g., serious illness in a family member, major holiday, vacation that cannot be rescheduled) without this being considered a protocol violation. Documentation to justify this delay should be provided.

To determine response via RECIST v1.1, patients will undergo radiographic imaging every 2 months (+/- 7 days) treatment for the first 8 cycles (beginning Day 1 Cycle 3) then every 3 cycles (beginning with Day 1 Cycle 9), until evidence of progression or relapse.

Agent	Dose	Route	Schedule
Enzalutamide	160 mg	PO	Daily

Note: If a patient is suspected to be pregnant, enzalutamide should be IMMEDIATELY discontinued and the study physician contacted. A positive urine test must be confirmed by a serum pregnancy test. If it is confirmed that the patients is not pregnant, the patient may resume dosing with enzalutamide.

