8.2 Dose Modifications

The following general guidelines apply to all dose modifications listed below

- Doses will not be re-escalated once reduced
- If dose reduction below dose level -2 is required, treatment with the agent will be discontinued.
- If treatment is held for more than four weeks due to toxicity, discontinue protocol therapy
- Each cycle is always 28 days regardless of dose interruption. (i.e., a 7 day interruption of a dose starting on day 15 of a cycle would mean that the dose is restarted on day 22 of the same cycle)
- If multiple adverse events are seen, administer dose based on greatest reduction required for any single adverse event observed. Reductions or increases apply to treatment given in the preceding cycle and are based on adverse events observed since the prior dose.

NOTE: AERS reporting may be required for some adverse events (See Section 9.0)

Dose level table for enzalutamide

Dose Level	enzalutamide
0 (starting dose)	160 mg/day
-1	120 mg/day
-2	80 mg/day

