8.2.3 Reversible posterior leukoencephalopathy syndrome (RPLS)

For signs and symptoms suggestive of reversible posterior leukoencephalopathy syndrome (RPLS) such as confusion, headache, seizures, and cortical blindness, hold enzalutamide for up to 4 weeks. Suspected RPLS should be investigated with MRI. If diagnosis of RPLS is confirmed, enzalutamide should be permanently discontinued. If RPLS is ruled out via MRI and signs and symptoms attributed to another cause, enzalutamide should resume.

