13.8 AE Stopping Rule

The stopping rule specified below is based on the knowledge available at study development. We note that the Adverse Event Stopping Rule may be adjusted in the event of either (1) the study re-opening to accrual after any temporary suspension or (2) at any time during the conduct of the trial and in consideration of newly acquired information regarding the adverse event profile of the treatment(s) under investigation. The study team may also choose to suspend accrual because of unexpected adverse event profiles that have not crossed the specified rule below

The study team will have regular toxicity calls to review overall toxicity, along with AERs reports.

Accrual will be temporarily suspended to this study if at any time we observe events considered at least possibly related to study treatment (i.e., an adverse event with attribute specified as "possible", "probable", or "definite") that satisfy the following criteria.

• For this study, unacceptable toxicity is defined as: treatment related deaths or seizures. If 1 or more patients out of the first 10 patients enrolled (or subsequently, if more than 10% of all patients) develop unacceptable toxicity, the study will be temporarily suspended until the review of all toxicity data is completed and a decision is made about whether it is safe to resume accrual. This decision will be made by consensus of the study team and CTEP.

In addition, any required reporting to the FDA will be made as per 21 CFR 312.32 by the pharmacovigilance executive officer and Alliance regulatory department.

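### Sections 8.2.2 and 8.2.3 give opposite dosing instructions after a seizure when MRI rules out RPLS and another cause is assigned

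*Combined protocol and SAP*

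**What the plan says.** Section 8.2.2 consists of a single instruction: "Discontinue enzalutamide for any seizure". It sets no condition on cause, attribution, grade or imaging result.

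Section 8.2.3 follows directly and deals with suspected RPLS. For suggestive signs and symptoms, it says, "such as confusion, headache, seizures, and cortical blindness, hold enzalutamide for up to 4 weeks". MRI is then to be done. Confirmed RPLS means permanent discontinuation. For the negative case the text is: "If RPLS is ruled out via MRI and signs and symptoms attributed to another cause, enzalutamide should resume". The section does not mention 8.2.2.

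Three other provisions bear on the question:

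- The general guidelines in 8.2 state: "If multiple adverse events are seen, administer dose based on greatest reduction required for any single adverse event observed".
- Section 7.0 states: "Patients will remain on therapy until progression of disease or development of unacceptable toxicities or patient or physician withdrawal".
- Section 13.8 states: "For this study, unacceptable toxicity is defined as: treatment related deaths or seizures". That sentence belongs to a rule whose opening words are "Accrual will be temporarily suspended to this study if at any time we observe events considered at least possibly related to study treatment".

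**The concern.** Seizure is the one sign in the 8.2.3 list that also has its own dosing rule, and that rule is absolute. A site that takes a seizure down the RPLS pathway arrives, after a negative MRI and an alternative explanation, at an instruction to restart the drug. A site that applies 8.2.2 never restarts it. Both would be following the written protocol.

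What is at stake is re-exposure of a patient who has had a seizure. The rest of the protocol treats seizure as a priority risk. Section 3.3.7 excludes patients with a history of seizures, 9.1 solicits seizures at baseline and in each cycle, and under 13.8 a single treatment-related seizure among the first 10 patients suspends accrual. Restarting after a seizure runs against all of this.

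**Working it through.** No arithmetic applies: the point depends on no sample size, error rate or event count. The check is to follow a patient who has had a seizure through both sections, and then to look for a provision that decides between them.

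**Step 1. Overlap of triggers.** Section 8.2.3 names four example signs: confusion, headache, seizures and cortical blindness. One of the four, seizures, is also governed by 8.2.2.

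**Step 2. Outcomes for a patient with a seizure.**

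| Outcome of work-up | 8.2.2 | 8.2.3 | Result |
|---|---|---|---|
| RPLS confirmed | Discontinue | Discontinue permanently | Agree |
| RPLS ruled out, another cause assigned | Discontinue | Resume | **Conflict** |
| RPLS ruled out, no other cause assigned | Discontinue | Silent | 8.2.2 stands alone |

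While the MRI is pending, neither section has the patient taking drug, so the difference in practice appears only in the final instruction, in one of the three outcomes.

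**Step 3. Whether discontinue in 8.2.2 could mean a temporary stop.** Section 8.2.1 says interrupt for a temporary stop and discontinue for hepatic failure; 8.2.3 says hold for a temporary stop. Section 7.0 does use discontinue for suspected pregnancy, where dosing may later restart, but there the route back is spelled out. Section 8.2.2 gives none, so it reads as a final stop.

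**Step 4. Whether 8.2.2 covers only drug-related seizures.** Its heading refers to toxicity, but its text covers every seizure. Where an attribution limit was wanted, as in 8.2.4, it was written in.

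**Step 5. What counts as another cause in 8.2.3.** In context it means a cause other than RPLS. The wording does not exclude enzalutamide itself, and Section 10.1 lists seizure and RPLS as separate known toxicities. Read literally, a drug-related seizure with a negative MRI also falls under the instruction to resume.

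**Step 6. Search for a tie-breaker.**

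- *8.2 general guideline.* It is written for several adverse events occurring together and for dose reductions. A seizure as the only sign is one event under two rules, which the guideline does not expressly reach.
- *7.0 with 13.8.* Therapy ends on unacceptable toxicity, and 13.8 counts seizures as such. But that definition is made for suspending accrual and is limited to events at least possibly related to treatment, and neither 7.0 nor 8.2 refers to it.

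Neither provision sets precedence between 8.2.2 and 8.2.3.

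**The case against.** The best answer is that the sections can be read together. On that reading 8.2.3 is a diagnostic work-up for one condition. Seizures appear only in an illustrative list, the hold exists because RPLS is suspected, and the last sentence merely lifts that hold. It does not cancel a separate ground for stopping. The seizure rule sits immediately above and is hard to miss. A drug-caused seizure is the core case of 8.2.2, so extending the resume sentence to it is strained. The general guideline, 7.0 and 13.8 all point toward stopping. On this view the defect is only a missing cross-reference.

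Much of this stands. A cautious physician would probably stop. Resumption is worded as should, and 7.0 allows physician withdrawal, so nobody is forced to re-treat. The event is rare and the harm falls on an individual patient.

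What does not stand is that the text already says this. Section 8.2.3 puts seizures alongside the other three signs, places them on a hold rather than a stop, and applies one resume instruction to all of them. The harmonised reading requires the reader to supply an exception, and a safety rule should not depend on each site noticing the clash and choosing the safer instruction.

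**Conclusion.** The concern holds. After a seizure with RPLS excluded by MRI and another cause assigned, 8.2.2 stops enzalutamide, 8.2.3 says it should resume, and no text decides between them. The conflict is confined to that one outcome.

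The documents give no basis for a probability. The below-1% category in Section 10.1 describes known drug toxicity and does not cap seizures attributed to something else. No endpoint, sample size or analysis is affected; the consequence is for the safety of an individual patient and for consistency between sites. It should be fixed, because following 8.2.3 as written would breach 8.2.2.

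The conclusion rests on reading discontinue in 8.2.2 as final and its scope as every seizure, whatever the cause. The wording supports both. If 8.2.2 was instead meant to allow a restart, the protocol would still need to say so.

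**What to change.** Let 8.2.2 govern and add one sentence at the end of 8.2.3:

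> Any patient with a seizure is discontinued under 8.2.2 regardless of MRI result; the resume instruction applies only to patients whose signs and symptoms did not include a seizure.

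MRI would still be done after a seizure when RPLS is suspected, for diagnosis and reporting. The change has no statistical cost. Its one downside is that a patient whose seizure had nothing to do with the drug loses access to it, which 8.2.2 already requires.

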8.2.3 Reversible posterior leukoencephalopathy syndrome (RPLS)

For signs and symptoms suggestive of reversible posterior leukoencephalopathy syndrome (RPLS) such as confusion, headache, seizures, and cortical blindness, hold enzalutamide for up to 4 weeks. Suspected RPLS should be investigated with MRI. If diagnosis of RPLS is confirmed, enzalutamide should be permanently discontinued. If RPLS is ruled out via MRI and signs and symptoms attributed to another cause, enzalutamide should resume.

8.2.4 Other Non-Hematologic Grade 3 or 4 Toxicity

For patients on both arms who experience a grade 3 or greater toxicity attributed to enzalutamide, enzalutamide should held for one week or until symptoms improve to \leq grade 2. Patients may be re-started on enzalutamide at one dose level reduction. If treatment is held for more than 4 weeks, discontinue protocol therapy.

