Enzalutamide is a strong CYP3A4 inducer and moderate CYP2C9 and CYP2C19 inducer. Enzalutamide reduced plasma exposure of midazolam (CYP3A4 substrate), warfarin (CYP2C9 substrate), and omeprazole (CYP2C19 substrate). Concomitant use of enzalutamide with narrow therapeutic index drugs that are metabolized by CYP3A4 (e.g. alfentanil, cyclosporine, dihydroergotamine, ergotamine, fentanyl, pimozide, quinidine, sirolimus, and tacrolimus), CYP2C9 (e.g. phenytoin, warfarin), and CYP2C19 (e.g. S-mephenytoin) should be avoided, as enzalutamide may decrease their exposure. If co-administration with warfarin cannot be avoided, conduct additional INR monitoring.

Pharmacokinetics

Absorption: rapid with time to peak concentration in 1 hour (range 0.5-3 hours). A high-fat meal did not alter the AUC to enzalutamide or N-desmethyl enzalutamide.

Distribution: 110 L; protein binding of parent drug is 97-98% to primarily albumin; protein binding of active metabolite is 95% to plasma proteins

Metabolism: Hepatic via CYP2C8 (formation of active metabolite N-desmethyl enzalutamide) and CYP3A4

Excretion: Primarily eliminated by hepatic metabolism. Following single oral administration of 14C-enzalutamide 160 mg, 85% of the radioactivity is recovered by 77 days post dose: Urine (71%), feces (14%) primarily as inactive metabolite

T1/2: Enzalutamide: 5.8 days (range 2.8-10.2 days); N-desmethyl enzalutamide: 7.8-8.6 days.

Adverse Events

Common known potential toxicities, > 10%:

Cardiovascular: Peripheral edema, hypertension

Central Nervous System: Fatigue, falling, headache, dizziness

Endocrine & Metabolic: Hot flash, weight loss

Gastrointestinal: Constipation, diarrhea, decreased appetite

Hematologic & Oncologic: Neutropenia

Neuromuscular & Skeletal: Weakness, back pain, arthralgia, musculoskeletal pain

Respiratory: Upper respiratory tract infection, dyspnea

Less common known potential toxicities, 1 to 10%:

Central Nervous System: Myasthenia, insomnia, anxiety, paresthesia, cauda equine syndrome, spinal cord compression, altered mental status, hypoesthesia, hallucination, and restless leg syndrome

Dermatologic: Pruritus, xeroderma

Endocrine & Metabolic: Gynecomastia

Gastrointestinal: Dysgeusia

Genitourinary: Hematuria, pollakiuria

Hematologic & Oncologic: Thrombocytopenia

Hepatic: Increased serum bilirubin

Infection: Infection

Neuromuscular & Skeletal: Bone fracture, stiffness Respiratory: Lower respiratory tract infection, epistaxis

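### Section 8.2.4 lets a toxicity hold end after one week or on improvement and names no recovery grade for restart, so read literally it allows re-dosing at grade 3-4

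*Combined protocol and SAP*

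**What the plan says.** Section 8.2.4 of the protocol covers non-hematologic toxicity of grade 3 or worse that is attributed to enzalutamide and has no rule of its own. It has three parts.

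- Hold: "enzalutamide should held for one week or until symptoms improve to" grade 2 or less.
- Restart: "Patients may be re-started on enzalutamide at one dose level reduction".
- Cap: a hold of more than 4 weeks ends protocol therapy.

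The general guidelines in Section 8.2 repeat the cap ("If treatment is held for more than four weeks due to toxicity, discontinue protocol therapy") and set a dose floor ("If dose reduction below dose level -2 is required, treatment with the agent will be discontinued"). They name no grade to which a patient must recover before restarting.

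The hepatic rule in Section 8.2.1 does name one: "Restart enzalutamide at one dose level reduction when ALT, AST, and bilirubin recover to grade 1".

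**The concern.** Two conditions joined by *or* are met when either one is met. A hold that lasts one week or until improvement is therefore over after one week, whatever the grade. The restart sentence could have closed the gap by naming a grade, but it does not.

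The first thing at stake is patient safety: the written rule permits re-exposure during an unresolved severe event that the investigator attributes to the drug. The second is consistency: two sites can read the same sentence differently and manage the same patient differently. The rule has a wide reach, because it covers every severe non-hematologic toxicity other than hepatic events, seizure and reversible posterior leukoencephalopathy syndrome (RPLS). That includes effects which Section 10.1 lists as common, such as fatigue and hypertension.

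**Working it through.** The plan gives no figure for this rule, so there is nothing to reproduce. The check is a reading of the text.

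**Step 1. How long does the hold last?** Let T be the number of days until the event improves to grade 2 or less. Three readings are possible:

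- A, literal (either limb ends the hold): hold = min(7, T).
- B, both limbs required: hold = max(7, T), capped at 28 days.
- C, recovery only: hold = T, capped at 28 days.

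| Time to grade 2 or less | A | B | C |
|---|---|---|---|
| T < 7 | restart allowed at T | restart allowed at day 7 | restart allowed at T |
| 7 < T ≤ 28 | restart allowed at day 7, still at grade 3-4 | restart allowed at T | restart allowed at T |
| T > 28 | restart allowed at day 7, still at grade 3-4 | discontinue | discontinue |

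Only reading A allows re-dosing before recovery, and reading A is what the words say.

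**Step 2. Does the restart sentence add a condition?** No. It gives permission and a dose step, for example from 160 to 120 mg/day, but no grade.

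**Step 3. Does the rest of Section 8.2.4 point to another reading?** Yes. Under A the required hold never exceeds 7 days, so the 28-day cap could apply only if a physician chose to hold for longer than the rule asks. Under B or C the cap has a clear purpose. This is evidence that A was not intended, but it does not show whether B or C was.

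**Step 4. Does another section supply a restart grade?**

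- Section 8.2, general guidelines: cap and dose floor, no grade.
- Section 8.2.1: grade 1, for hepatic events only.
- Section 7.0: "Patients will remain on therapy until progression of disease or development of unacceptable toxicities or patient or physician withdrawal". No grade.
- Section 12.1.1 (intolerable toxicity) and Section 12.3 (detriment to the patient's health): grounds for stopping, no grade.
- Section 5.0: leaves monitoring to institutional guidelines and physician judgment.
- Section 13.8: regular toxicity calls, and suspension of accrual for treatment-related deaths or seizures. It does not govern restart in an individual patient.

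None fills the gap.

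**Step 5. Does any design figure depend on the rule?** No. The two-stage design in Section 13.2 (21 then 41 patients, response rates of 5% against 20%) does not use the hold or restart rule.

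**The case against.** The strongest case against is that a sensible physician would not read the rule this way. Restart is optional and at a lower dose. A patient still at grade 3-4 on day 8 arguably still meets the trigger for the hold, so it would simply continue. A general guideline in Section 8.2 ties dose changes to events seen since the previous dose, although it sits in the bullet on multiple adverse events and its scope is arguable. Seizure means permanent discontinuation, and hepatic events and RPLS have their own rules. The general stopping provisions also apply.

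Most of this stands. It makes re-dosing of an unresolved grade 4 event unlikely, and it rules out the stronger claim that the protocol instructs sites to re-dose. It does not remove the gap. Each safeguard relies on judgment, none states a restart grade, and the several plausible readings are themselves the consistency problem.

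A reader might infer three further things that the documents do not support.

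- *That Section 8.2.3 is a second contrasting recovery rule.* It is not. It says "If RPLS is ruled out via MRI and signs and symptoms attributed to another cause, enzalutamide should resume", which is a diagnostic condition; the symptoms need not have improved.
- *That residual drug makes one week unsafe.* Section 10.1 gives "T1/2: Enzalutamide: 5.8 days (range 2.8-10.2 days); N-desmethyl enzalutamide: 7.8-8.6 days", so a week is a short washout. But no section links drug level to toxicity grade, and a recovery-based rule lets an early improver restart before day 7, with more drug on board. The half-lives therefore do not support the fix.
- *That the extra exposure can be counted in doses or milligrams.* Any count depends on whether a persisting event re-triggers the hold, which the text does not settle.

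**Conclusion.** The point holds as a wording fault in a safety rule and should be corrected. As written, Section 8.2.4 permits restart at grade 3-4 after one week, and nothing else in the protocol sets a restart grade. The cap and the word *may* suggest that this was not intended.

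Its effect cannot be expressed in patients or doses: that would need the frequency and duration of these events and each site's reading of the sentence, none of which the documents give. The primary endpoint, error rates and sample size are unaffected. The conclusion rests only on the ordinary meaning of *or* and on the absence of a restart grade elsewhere. It does not assume that any site would follow the literal reading.

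**What to change.** Replace the text of Section 8.2.4 with:

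> For patients with a non-hematologic toxicity of grade 3 or greater that is attributed to enzalutamide (other than those covered in 8.2.1 to 8.2.3), hold enzalutamide until symptoms improve to grade 2 or less. Patients may then be re-started at one dose level reduction. If symptoms have not improved to grade 2 or less within 4 weeks, discontinue protocol therapy.

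This keeps the trigger (grade and attribution), the physician's option not to restart, the grade 2 threshold, the single dose step and the 4-week limit. It removes only the one-week limb. It also drops the stray reference to two arms, since the trial has one. Early improvers may restart as soon as the current text already allows; if the sponsor meant one week as a minimum, that should be stated as a separate condition.

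The cost is one wording change. Some holds will be longer, and confirming recovery will usually take one unscheduled contact or laboratory test. A few patients with slow-resolving events may be discontinued at 4 weeks, which matters in a disease with no standard drug therapy, but that cap is already in Sections 8.2 and 8.2.4. No patients are added and the design does not change.
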